#### 14.6.2.4. Exposure and Compliance

Exposure and Compliance																					
Exposure																					

 
Exposure (days) = Treatment stop date – treatment start date + 1 day
 
																					
Compliance																					

 
Compliance will be calculated based on data recorded in the Study Treatment/Compliance Record eCRF pages (blinded and unblinded) and will only be calculated for subjects with a non-missing treatment start date, and will not be calculated after a subject's treatment stop date, or study conclusion date for subjects who have a non-missing treatment start date and a missing treatment stop date.
 
A compliance category will be assigned to each study treatment exposure visit according to the following tables. Exposure records corresponding to periods of dose hold/zero-dose as assigned by the IRT will be categorized in the compliant category (given no active treatment doses are taken) and any gaps between exposure records will be categorized in the under compliant category. 
 
Daprodustat and rhEPO 
  
 Under Compliant	Compliant	Over Compliant	
   
 Compliance for the exposure record < 80%	Compliance for the exposure record <math>\geq</math> 80% and <math>\leq</math> 120%	Compliance for the exposure record > 120%	
 
 Where compliance for each visit is calculated as (Total Cumulative Dose/Planned Dose)x100	
  
 
 
 
 
			Under Compliant	Compliant	Over Compliant	Compliance for the exposure record < 80%	Compliance for the exposure record $\geq$ 80% and $\leq$ 120%	Compliance for the exposure record > 120%	Where compliance for each visit is calculated as (Total Cumulative Dose/Planned Dose)x100												
Under Compliant	Compliant	Over Compliant																			
Compliance for the exposure record < 80%	Compliance for the exposure record $\geq$ 80% and $\leq$ 120%	Compliance for the exposure record > 120%																			
Where compliance for each visit is calculated as (Total Cumulative Dose/Planned Dose)x100																					

 
Planned Dose [1] 
  
 Visit	Daprodustat TIW dose	rhEPO Weekly dose	
   
 Completed Day 1	Assigned dose x 6	Assigned dose x 2	
 
 Completed Week 2 – Week 6	Assigned dose x 6	Assigned dose x 2	
 
 Completed Week 8 – Week 48	Assigned dose x 12	Assigned dose x 4	
 
 Uncompleted Visit.	Expected Number of doses taken (dose stop date – dose start date+1)*0.428571428	Expected Number of doses taken (dose stop date – dose start date+1)* 0.1428571428	
 
 Assigned dose * Expected Number of doses	Assigned dose * Expected Number of doses	
 
 0.428571428 is 3 divided by 7	0.1428571428 is 1 divided by 7	
  
 
 
			Visit	Daprodustat TIW dose	rhEPO Weekly dose	Completed Day 1	Assigned dose x 6	Assigned dose x 2	Completed Week 2 – Week 6	Assigned dose x 6	Assigned dose x 2	Completed Week 8 – Week 48	Assigned dose x 12	Assigned dose x 4	Uncompleted Visit.	Expected Number of doses taken (dose stop date – dose start date+1)*0.428571428	Expected Number of doses taken (dose stop date – dose start date+1)* 0.1428571428	Assigned dose * Expected Number of doses	Assigned dose * Expected Number of doses	0.428571428 is 3 divided by 7	0.1428571428 is 1 divided by 7
Visit	Daprodustat TIW dose	rhEPO Weekly dose																			
Completed Day 1	Assigned dose x 6	Assigned dose x 2																			
Completed Week 2 – Week 6	Assigned dose x 6	Assigned dose x 2																			
Completed Week 8 – Week 48	Assigned dose x 12	Assigned dose x 4																			
Uncompleted Visit.	Expected Number of doses taken (dose stop date – dose start date+1)*0.428571428	Expected Number of doses taken (dose stop date – dose start date+1)* 0.1428571428																			
	Assigned dose * Expected Number of doses	Assigned dose * Expected Number of doses																			
	0.428571428 is 3 divided by 7	0.1428571428 is 1 divided by 7																			

[1] Assigned Dose: Dose assigned by the IRT as the start of the Visit.
 
 
Actual Dose
 
																					

CONFIDENTIAL

204837

Exposure and Compliance		
Duration of Exposure Record	Daprodustat (mg)	rhEPO (U)
Day 1 to Week 48 individual dose record	Container Dose x Number of tablets taken	Dose recorded on eCRF [2]

[2] DOSE entered on open eCRF or if "Did subject receive correct treatment? is No then DOSE from unblinded eCRF.
 
Each visit will fall into one of the 3 categories and the percentage of time that a subject spent in each of the 3 categories above or with missing compliance data will be determined using the duration of treatment in each visit with the total duration of treatment.
 
 
Compliance will be summarized for the following time periods: Day 1 - < Week 28, Week 28 - ≤ Week 52, and Day 1 - ≤ Week 52 (Overall compliance).
 
Within each period, the percentage of time that a subject spent in each of the 3 categories above or with missing compliance data will be determined.
 
		

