Hospitalization or kidney transplant ²⁶			X	X	X	X	X

DBP, diastolic blood pressure; ECG, electrocardiogram; EDW, estimated dry weight; FSH, follicle stimulating hormone; HbA1c, glycated hemoglobin; HR, heart rate; hsCRP, high sensitivity C-reactive protein; iPTH, intact parathyroid hormone; PD, pharmacodynamics; PK, pharmacokinetics; SBP, systolic blood pressure; UIBC, unsaturated iron binding capacity; VEGF, vascular endothelial growth factor; WOCBP, woman of childbearing potential.

Note: Pre-dialysis assessments should be performed in the following order, where applicable: patient reported outcomes, ECG, BP/HR, blood sample collection.

- All assessments to be performed pre-dose.
- If additional study treatment is required prior to the next scheduled study visit, it is not necessary to perform the unscheduled visit assessments other than dispensing study treatment.
- Study treatment will be dispensed every 4 ± 1 weeks, with the exception that it may be every 2 weeks ± 3 days up to the Week 6 visit. An IRT transaction will be required to dispense study treatment. Additional IRT transactions may occur if needed to dispense additional study treatment.
- In circumstances where randomization of an eligible participant cannot be completed at the Day 1 visit, the visit may be rescheduled up to 1 week later. Clinical laboratory assessments performed at the original visit, no more than 1 week prior, do not need to be repeated, except for the HemoCue hemoglobin and the Q2 hemoglobin.
- Study treatment will be dispensed, i.e., allocated to a specific participant, and stored at the dialysis center or research site. Participant may take study treatment tablets at home in preparation for PD visit. See Section 7 for further study treatment details.

6. In circumstances where a new supply of study treatment (including a new dose) cannot be dispensed on the day of the study visit, the new supply of study treatment can be dispensed at the next dialysis session. Prior study treatment should be continued unless on dose interruption, e.g., Hgb ≥ 12 g/dL. Compliance is deferred until study treatment is returned.
7. At the Week 2, Week 6 or unscheduled visits, if dose is not changed, new study treatment does not need to be dispensed and use of existing study treatment is continued. Compliance checking is required if new study treatment is dispensed.

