9. STUDY ASSESSMENTS AND PROCEDURES

- Study procedures and their timing are summarized in the SoA (Section 2). Pre-dialysis assessments should be performed in the following order, where applicable: patient reported outcomes, ECG, BP/HR, blood sample collection.
- Protocol waivers or exemptions are not allowed.
- Immediate safety concerns should be discussed with the sponsor immediately upon occurrence or awareness to determine if the participant should continue or discontinue study treatment.
- Adherence to the study design requirements, including those specified in the SoA (Section 2), is essential and required for study conduct.
- All screening evaluations must be completed and reviewed to confirm that potential participants meet all eligibility criteria. The investigator will maintain a screening log to record details of all participants screened and to confirm eligibility or record reasons for screening failure, as applicable.
- All visits should be referenced back to the Randomization visit (Day 1). The allowable visit window is ± 3 days for Week 2 to Week 8 visits, and ± 1 week for all other visits; however, study visits must be no more than 5 weeks apart.
- In exceptional circumstances, minor changes to visit structure may be permitted after consultation with the Medical Monitor.
- Because Hgb levels become more variable with increased time between dialysis sessions, the designated study visit should occur during the dialysis session with the shortest interval from the previous session. For participants on a three- to five-times weekly dialysis schedule, the designated study visit must not occur on the first dialysis session of the week, i.e., the dialysis session immediately following the longest interval between dialysis sessions. For example, if on a Monday-Wednesday-Friday schedule, the study visit should be on Wednesday or Friday.

- Procedures conducted as part of the participant's routine clinical management (e.g., renal and adrenal gland ultrasound) and obtained before signing of the ICF may be utilized for screening or baseline purposes provided the procedure met the protocol-specified criteria and was performed within the time frame defined in the SoA (Section 2).
- The maximum amount of blood collected from each participant over the duration of the study, including any extra assessments that may be required, will not exceed 375 mL. This blood volume does not include any repeat or unscheduled samples that may be taken.

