#### **6.2.6. Exposure and Treatment Compliance**

Months of exposure (see Section 14.6.2.4) will be summarized using mean, standard deviation, minimum, P25, median, P75, and maximum by treatment group and overall. Additionally, the number and percentage of subjects with exposure  $\leq 6$ -month and  $> 6$ -month will be provided by treatment group and overall.

A listing of exposure data will be provided. This listing will include treatment, site ID, unique subject ID, Subject ID, dose start date, dose stop date, duration of time on dose, dose, dose units, dose form, route of administration, and flags for missed dose, zero dose and dose hold. Exposure data from the unblinded eCRF will be listed separately.

Percent compliance will be estimated by  $100 * (\text{Total Cumulative Dose} / \text{Planned Dose for a specific time period})$ . The number and percentage of subjects in each study treatment compliance category (see Section 14.6.2.4) during the study will be summarized by treatment group for the following time periods: Day 1 < Week 28, Week 28 -  $\leq$  Week 52, and Day 1 -  $\leq$  Week 52 (Overall Compliance).

The percentage of time that subjects spend in each of the three compliance categories, (i.e., under compliant, compliant and over compliant) will be summarized using mean, standard deviation, minimum, P25, median, P75, and maximum by treatment group for the following time periods: Day 1 < Week 28, Week 28 -  $\leq$  Week 52, and Day 1 -  $\leq$  Week 52 (Overall Compliance).

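### SAP 14.6.2.4 fixes the planned dose of a completed visit whatever its length, so some fully adherent visits are labelled under or over compliant in a descriptive table (minor)

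*SAP*

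**What the plan says.** SAP 14.6.2.4 (Exposure and Compliance) gives planned dose by type of visit. A completed Week 8 to Week 48 visit has "Assigned dose x 12" for daprodustat and four times the assigned weekly dose for rhEPO. Completed Day 1 to Week 6 visits use 6 and 2. Only an uncompleted visit is scaled by days, at 3/7 per day for daprodustat and 1/7 for rhEPO. The SAP does not define a completed visit; the natural reading is that the participant reached the next visit on treatment.

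The score is per visit: "Where compliance for each visit is calculated as (Total Cumulative Dose/Planned Dose)x100". Below 80% is under compliant and above 120% is over compliant. SAP 14.6.2.4 adds: "Each visit will fall into one of the 3 categories". Time in each category is then weighted by the actual duration of the visit. SAP 6.2.6 summarises by treatment group: "The percentage of time that subjects spend in each of the three compliance categories". The same section also defines a percentage over a whole period, with the denominator "Planned Dose for a specific time period".

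On visit length, the notes to the protocol's Schedule of Activities (Section 2) say: "Study treatment will be dispensed every 4 ± 1 weeks". Protocol Section 9 allows a window of one week either side for visits after Week 8 and adds that "study visits must be no more than 5 weeks apart".

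**The concern.** The multipliers 12 and 4 are right for a 28-day visit and for no other length. The numerator grows with the days between visits and the denominator does not, so the score partly measures visit timing.

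Once-weekly epoetin (10,000 U/week or less in protocol Table 6) is the more exposed regimen. Its count can only be 3, 4 or 5 over three to five weeks, and both 3/4 and 5/4 lie outside 80-120%. Only the epoetin arm has once-weekly active dosing, so the artefact need not fall equally on the two arms. At stake is the reading of one by-arm adherence table.

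**Working it through.** **Inputs.** Multipliers 12 and 4 (6 and 2 for two-week visits), daily factors 3/7 and 1/7, and cut-offs of 80% and 120%: SAP 14.6.2.4. Permitted interval of 21 to 35 days: protocol Sections 2 and 9. Epoetin once weekly up to 10,000 U/week and three times weekly from 12,000 U/week: protocol Table 6. Epoetin given during dialysis: protocol Table 3. Study visits on Wednesday or Friday for a Monday-Wednesday-Friday patient: protocol Section 9.

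**Reproducing the plan's figures.** 28 × 3/7 = 12 and 28 × 1/7 = 4; 14 × 3/7 = 6 and 14 × 1/7 = 2. The fixed multipliers are the daily rule evaluated at exactly 28 and 14 days.

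**Full adherence at the permitted extremes.**
- 21 days: 9/12 = 3/4 = 75%, under compliant.
- 35 days: 15/12 = 5/4 = 125%, over compliant.

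**Whole-dose counts** for a Monday-Wednesday-Friday patient. A dose on the visit day counts to that visit, and the next visit day counts to the next. Cells show doses and score; bold marks a wrong label.

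| Gap (days) | Daprodustat (of 12) | Epoetin weekly, Mon or Fri (of 4) | Epoetin weekly, Wed (of 4) |
|---|---|---|---|
| 21 | **9, 75%** | **3, 75%** | **3, 75%** |
| 23 | 10, 83% | **3, 75%** | 4, 100% |
| 26 | 11, 92% | 4, 100% | **3, 75%** |
| 28 | 12, 100% | 4, 100% | 4, 100% |
| 30 | 13, 108% | 4, 100% | **5, 125%** |
| 33 | 14, 117% | **5, 125%** | 4, 100% |
| 35 | **15, 125%** | **5, 125%** | **5, 125%** |

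Three-times-weekly epoetin behaves like daprodustat. Two-week visits have the same fault. At 12 and 16 days daprodustat scores 5/6 = 83% and 7/6 = 117%, while weekly Wednesday epoetin scores 1/2 = 50% and 3/2 = 150%.

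**Period level.** Visits are anchored to Day 1, so the Week 28 to Week 52 span is 24 weeks give or take 2. At constant dose an adherent participant who stays through it scores between 22/24 = 92% and 26/24 = 108%.

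**Check on the uncompleted-visit rule.** It runs from dose start to dose stop. If those are the first and last dose dates, n weekly doses span 7n − 6 days. Four doses span 22 days and score 4/(22/7) = 127%. Copying that rule to completed visits would therefore replace one error with another.

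**The case against.** The strongest reply is that little depends on this. The table has no test, and no decision in the plan is shown to use it. For daprodustat and three-times-weekly epoetin, only a visit a full week short or long is mislabelled. A patient who always attends on the same weekday has gaps of 21, 28 or 35 days only, so the once-weekly problem at intermediate gaps arises only when the visit weekday changes. All of that stands, and it limits the severity. It does not rescue the rule, because every gap in the table is permitted and the labels are wrong for patients who missed nothing.

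Three stronger readings are tempting and are not supported.
- A reader might infer an adherence bias of known size against the epoetin arm. The documents give neither the distribution of visit gaps nor the share of participants on once-weekly epoetin, so any percentage would rest on invented inputs.
- A reader might infer that the per-protocol set is distorted through exclusion 03 (SAP 14.1.1). That criterion refers to the compliance category during the EP, which reads most naturally as the period-level percentage of SAP 6.2.6. It is also a criterion under which a subject may be excluded, subject to blinded review. Someone who stops after one 35-day EP visit would score 15/12 = 125% for the period, but would already meet exclusion 02 (fewer than 5 of 7 evaluable values).
- A reader might infer an effect on the efficacy results. The primary analysis uses Hgb regardless of adherence, and the IV iron endpoint uses treatment dates. Neither uses these labels.

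**Conclusion.** The derivation is wrong as written and easy to correct. It mislabels fully adherent visits of 21 and 35 days on either drug, and once-weekly epoetin visits at some gaps as little as two days off schedule. The effect is confined to the descriptive percentage-of-time table. Its frequency, overall or by arm, cannot be computed. The conclusion rests on the natural reading of a completed visit and, for the intermediate gaps, on a Monday-Wednesday-Friday patient whose visits move between Wednesday and Friday. Severity is minor.

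**What to change.** 1. For all completed visits, including two-week visits, set planned doses to interval days × 3/7 (daprodustat) or × 1/7 (rhEPO weekly dose). Run the interval from the first dose record under the visit, given or flagged as missed, to the day before the first dose record under the next visit. Missed doses still count against the participant, because the exposure listing in SAP 6.2.6 carries "flags for missed dose, zero dose and dose hold".
2. If the next visit is a hold or zero dose, end the interval the day before that record starts. For once-weekly dosing this can cut too soon after the last dose: a 28-day Friday-to-Friday visit with Wednesday doses leaves 23 days, and 4/(23/7) = 122%. Rule 3 is safer in that case.
3. For the last visit on treatment and for uncompleted visits, end the interval at the last dose record (given or flagged as missed) plus the gap factor in SAP 14.6.2.1: 6 days once weekly, 1.33 days three times weekly. Four weekly doses then span 22 + 6 = 28 days and score 100%. Three-times-weekly dosing scores 88-111% for 1 to 15 doses.
4. Define a completed visit, and state in one sentence that exclusion 03 uses the EP-level percentage. The latter is a clarification only.

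Under rule 1 with a fixed dosing weekday, adherent visits at gaps of 8 to 35 days score 100% (once weekly) or 93-106% (three times weekly). The 26- and 30-day Wednesday cases become 3/(21/7) and 5/(35/7), both 100%.

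One weakness remains. A visit holding a single weekly dose can still fall outside 80-120% if the next dose moves by two days: 1/(9/7) = 78% or 1/(5/7) = 140%. Pool such a visit with the adjacent one. With two or four doses the same shift is tolerated (14/16 = 88% and 14/12 = 117%; 28/30 = 93% and 28/26 = 108%).

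The cost is one reworked derivation and two clarifying sentences. No new data are needed: SAP 14.6.3.5 says sites complete an exposure record for each dose taken or planned.

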### 14.6.3. Efficacy

#### 14.6.3.1. Hemoglobin Endpoints

Hemoglobin Values
Central Laboratory and HemoCue Hgb Values

 
When source of Hgb measurement is not specified: 
 
For reporting purposes, central laboratory Hgb values will be used, unless otherwise specified. However, if a central laboratory Hgb value is missing, a corresponding non-missing HemoCue Hgb value will be used. This approach will be used for the primary Hgb analysis.
 
 
 
Some displays may be created for either central laboratory Hgb values only or HemoCue Hgb values only. The central laboratory summary will be considered the primary summary in this case.
 

Evaluable Hemoglobin Values

 
Evaluable Hgb values are on-treatment Hgb values (see Section 14.4.1) that are not taken within the 8 weeks following a red blood cell transfusion, a whole blood transfusion, or a non-randomized ESA treatment which occurs on or after the randomization date.
 
Red blood cell transfusions, whole blood transfusions and non-randomized ESA treatments occurring on or after the randomization date are identified by comparing the start and stop date of the respective transfusion or ESA concomitant medication record to the randomization date.
 

Imputed Hemoglobin Values

 
For each missing value between baseline to Week 52 (inclusive), 200 imputed values will be generated using the multiple imputation method (see Section 7.1.5). The average of these 200 imputed values will be used as the value for this missing value in the summary tables and figures.
 

CONFIDENTIAL

204837

Hemoglobin Values					

 
For primary efficacy Hgb analysis and the corresponding subgroup analyses using all available observed and imputed Hgb values (on and off-treatment), Rubin's rules [Rubin, 1987] will be used to combine results of the imputed datasets using SAS PROC MIANALYZE procedure.
 
					
EP Hemoglobin Value for Primary Hgb Analysis					

 
For each subject, the mean of all available (on and off treatment) Hgb values during the EP (See Section 14.6.1) including any imputed and unscheduled Hgb values that were taken during this time period.
 
Should the assessment dates for Hgb values from the Early Treatment Discontinuation visit fall within the EP, then these values will be included as unscheduled Hgb values. Hgb values from the Follow-up visit will not be included in the EP mean.
 
					
EP Hemoglobin Value for While On-Treatment Evaluable Hgb Supportive Analysis					

 
For each subject, the mean of all evaluable Hgb values during the EP (See Section 14.6.1), including any evaluable unscheduled Hgb values that were taken during this time period.
 
Should the assessment dates for Hgb values from the Early Treatment Discontinuation visit fall within the EP, then these values will be included as unscheduled Hgb values. Hgb values from the Follow-up visit will not be included in the EP mean.
 
					
EP Hemoglobin Value for Alternative EP Supportive Analyses					

 
For each subject, the mean of all Hgb values during the Alt. EP (See Section 14.6.1), including any imputed and unscheduled Hgb values that were taken during this time period. This analysis will be conducted using all available (on and off treatment) Hgb values and separately using evaluable Hgb values only.
 
Should the assessment dates for Hgb values from the Early Treatment Discontinuation visit fall within the Alt. EP, then these values will be included as unscheduled Hgb values. Hgb values from the Follow-up visit will not be included in the Alt. EP mean.
 
					
Use of Unscheduled Hemoglobin Values and Multiple Hgb Values on the Same Date					

 
The scenarios outlined below provide guidance on the use of unscheduled Hgb values and multiple Hgb values occurring on the same date. Each row represents a single calendar date.
 
Rows outlining scenarios where there is at least one central lab Hgb and at least one HemoCue Hgb on the same date apply only for the derivation of Hgb values to be used in the primary Hgb analysis, where central lab values are used if they are available and if the central lab value is missing, then a corresponding non-missing HemoCue Hgb value is used.
 
Rows outlining scenarios involving combinations of scheduled and unscheduled Hgb values of the same type apply to all Hgb summaries and analysis.
 
					
Scheduled Central Lab Hgb Value	Unscheduled Central Lab Hgb Value	Scheduled HemoCue Hgb Value	Unscheduled HemoCue Hgb Value	Value to Use	Type/Label
x				Scheduled central lab Hgb value	Scheduled visit
	x			Unscheduled central lab Hgb value	Unscheduled
		x		Scheduled HemoCue Hgb value	Scheduled visit
		multiple 		Average of scheduled HemoCue Hgb values	Scheduled visit
			x	Unscheduled HemoCue Hgb value	Unscheduled
	multiple			Average of unscheduled central lab Hgb values	Unscheduled

CONFIDENTIAL

204837

Hemoglobin Values					
			multiple	Average of unscheduled HemoCue Hgb values	Unscheduled
x	x			Average of central lab Hgb values	Scheduled visit
x		x		Scheduled central lab Hgb value	Scheduled visit
x			x	Scheduled central lab Hgb value	Scheduled visit
	x	x		Unscheduled central lab Hgb value	Unscheduled
	x		x	Unscheduled central lab Hgb value	Unscheduled
		x	x	Average of HemoCue Hgb values	Scheduled visit

1: The dose adjustment algorithm will require sites to obtain two HemoCue Hgb values at some visits.

Time In Range
Time in Range During the EP

 
Number of days that a subject's evaluable Hgb is within the analysis range of 10-11.5 g/dL inclusive during the EP (See Section 14.6.1), including any unscheduled evaluable Hgb values that were taken during this time period.
 
Use of unscheduled Hgb values follows the scenarios for unscheduled and multiple Hgb values.
 
Linear interpolation is used to estimate Hgb between visits, accounting for any intermittent missing values (Rosendaal, 1993).
 

Percent Time in Range During the EP

 
Time in Range During the EP / [Earlier of (Treatment Stop Date+1, Week 52 visit date) – Week 28 visit date]
 
Note: Percent time in/below/above range during the EP is only defined for subjects with a Treatment Stop Date that is after their Week 28 visit date, and have at least two evaluable Hgb values on different days, where at least one evaluable Hgb value is contained within the EP and another evaluable Hgb value occurs within the range of the Week 16 visit through 4 weeks following the Week 52 visit, inclusive.
 

